## **8.4 Safety Monitoring Plan**

The plan for ensuring subject safety will include the following elements:

1. Clinical procedures will only be performed by properly trained personnel who are qualified by training and licensure to perform the procedures.
2. Investigator and all study personnel have completed required training regarding Human Subject Protections. All personnel will comply with all related regulations and laws.

3. Patients will be rigorously screened against inclusion/exclusion criteria to ensure that their participation is safe.
4. Adverse events and SAEs will be assessed and followed throughout study. Subjects will have contact information to enable them to contact study personnel easily and quickly.
5. Study data and information will be kept confidential and managed in accordance with requirements of Health Insurance Portability and Accountability Act of 1996 (HIPAA). All data will be stored in locked offices and not released without subject permission.
6. Subject may discontinue participation at any time, for any reason. Any subject who fails to complete the research procedures within acceptable parameters, or is unable to safely tolerate participation in the study will be withdrawn.
7. Institutional Review Board approval will be obtained.
8. Monitoring will be conducted by an external Data and Safety Monitor as described in the Data and Safety Monitoring Plan (appendix A).

#### **8.4.1 Anticipated Risks / Risk Mitigation**

##### **8.4.1.1 Venipuncture**

The risks of venipuncture are transient pain, bleeding, lightheadedness, bruising, possible vasovagal reaction, and infection. Only trained certified nursing assistants, nurses, nurse practitioners, or physicians will be allowed to perform venipuncture to minimize the risk of complication.

##### **8.4.1.2 pQCT and DXA**

The pQCT and DXA scan will expose the subject to ionizing radiation. The level of exposure for this study will be approximately 3% of that received from natural sources of radiation by a northern US resident in 1 year. Trained staff will perform the scans to minimize the risk of additional exposure.

##### **8.4.1.3 Provisions to Monitor the Data to Ensure the Safety of Subjects**

Genetic studies have raised concern as to whether the studies would place research subjects at risk for discrimination based on genetics. The federal Genetic Information Nondiscrimination Act (GINA) was passed to address this concern. GINA makes it illegal for medical insurance companies and most employers to discriminate based on genetic information. The protections of GINA do not apply to life, disability, or long-term-care insurance.

#### **8.4.2 Study Stopping Rules**

This study may be terminated by the PI at any time. Reasons for terminating the study may include the following:

- The incidence or severity of AEs in this or other studies indicates a potential health hazard to subjects.
- Subject enrollment is unsatisfactory.
- Data recording is inaccurate or incomplete.
- 1 patient develops a CTCAE Grade 4 or higher.

#### **8.4.3 Anticipated / Expected Adverse Events**

The following AEs have been reported in individuals treated with ACTIMMUNE: fever (52%), headache (33%), rash (17%), chills (14%), injection-site erythema or tenderness (14%), fatigue (14%), diarrhea (14%), vomiting (13%), and nausea (10%). Less common adverse events observed more frequently in the IFN- $\gamma$  1b group compared with placebo (occurring in <10% of patients) included myalgia, arthralgia, back pain, abdominal pain, and depression.

Adverse events related to osteopetrosis are expected. These expected events include but are not limited to, pain, fracture, infection, osteonecrosis, anemia, neutropenia, thrombocytopenia, hepatosplenomegaly, cranial nerve impingement, and hypocalcemia. These events will be considered expected for the purposes of expedited SAE reporting.

### **8.5 Data Safety Monitoring Plan**

Data safety monitoring plan is described in detail in Appendix A.

## **9 Data Handling and Record Keeping**

### **9.1 Confidentiality**

Study data and information will be kept confidential and managed in accordance with requirements of Health Insurance Portability and Accountability Act of 1996 (HIPAA). We will follow institutional policies regarding HIPAA, we will answer any questions/concerns the subjects and their parents may have in regards to their privacy, address items, and document. If at any time subject/parent/family/ or child appear uneasy during exams, questions, etc. the team member will stop the visit to refer to PI or doctor performing visit to determine if the study visit can continue. Research team is permitted to access sources of information about the subjects for research purposes only, document all requests if not in protocol.

HIPAA regulations require a signed subject authorization informing the subject of the following:

- What protected health information (**PHI**) will be collected from subjects in this study
- Who will have access to that information and why
- Who will use or disclose that information
- The rights of a research subject to revoke their authorization for use of their PHI.

In the event that a subject revokes authorization to collect or use PHI, the Investigator, by regulation, retains the ability to use all information collected prior to the revocation of subject authorization. For subjects that have revoked authorization to collect or use PHI, attempts should be made to obtain permission to collect at least vital status (i.e., that the subject is alive) at the end of their scheduled study period.

The samples sent to laboratories will include the subject's ID number and not their name. Those who have access to data and specimens are the research team who all have HIPAA training; these same people are responsible for receipt and/or transmission of data and specimens.

All interactions with the subject and his/her parents will take place in a private setting, e.g., a private exam room.

The genetic information obtained in this study is kept in strict confidence. The laboratories in which genotyping and assays are performed use only study ID codes and no other identifiers. The information is identified in the database by a unique code. The genotyping results are merged with the phenotype data for statistical genetic analysis using only study ID codes to identify individuals. We will secure hard copy information with keys and computer databases with password protection so that only research personnel related to this project will have access to information.

## **9.2 Source Documents**

*Source Data* are the clinical findings and observations, laboratory and test data, and other information contained in *Source Documents*. *Source Documents* are the original records (and certified copies of original records); including, but not limited to, hospital medical records, physician or office charts, physician or nursing notes, subject diaries or evaluation checklists, pharmacy dispensing records, recorded data from automated instruments, x-rays, etc. When applicable, information recorded on the CRF shall match the *Source Data* recorded on the *Source Documents*.

## **9.3 Case Report Forms**

The study CRF is the primary data collection instrument for the study. All data requested on the CRF must be recorded. All missing data must be explained. If a space on the CRF is left blank because the

procedure was not done or the question was not asked, "N/D" will be entered. If the item is not applicable to the individual case, "N/A" will be entered. All entries should be printed legibly in black ink. If any entry error has been made, to correct such an error, a single straight line will be drawn through the incorrect entry and the correct data entered above it. All such changes must be initialed and dated. DO NOT ERASE OR WHITE OUT ERRORS. For clarification of illegible or uncertain entries, the clarification will be printed above the item, then initialed and dated.

A Case Report Form will be completed for each subject enrolled into the clinical study. The Investigator-Sponsor will review, approve and sign/date each completed CRF; the Investigator-Sponsor's signature serving as attestation of the Investigator-Sponsor's responsibility for ensuring that all clinical and laboratory data entered on the CRF are complete, accurate and authentic.

All data including source documents and CRFs will be maintained in a locked filing cabinet in a locked office with limited access to only those involved in the research. Individual subject files will be labeled with the subjects unique study identification number and not their name.

#### **9.4 Clinical Reports**

An annual progress report will be submitted to the funding source and the IRB. Investigators will submit a final report of the clinical study to the reviewing IRB within 3 months of termination or completion of the clinical study or the Investigator's part of the clinical study.

#### **9.5 Records Retention**

The Investigator-Sponsor will maintain a file of all documents concerning the use of human subjects in research for 3 years from completion of IRB related work and 6 years for HIPAA.

#### **9.6 Data and Specimen Banking**

Stored samples will be identified by an indirect identifier (study ID) indefinitely. The study PI and study coordinator will have access to the link between subject information and study ID.

If stored samples are used in the future to look at new markers the subject or parent/guardian will not be notified nor will they receive the results from the analysis. If the samples are used by other research groups for analysis, the subject and guardian will not be notified. However, any samples that are sent to another researcher will be identified only with a number and will not be able to be traced back to the subject. The subject will not be identified in any publication or report from this study. The subject or guardian can request that blood, urine, RNA, and DNA samples be destroyed at any time by contacting the study PI.

## **10 Study Auditing, and Inspecting**

The Investigator will permit study-related monitoring, audits, and inspections by the IRB, government regulatory bodies, and University compliance and quality assurance groups of all study related documents (e.g., source documents, regulatory documents, data collection instruments, study data etc.). The Investigator will ensure the capability for inspections of applicable study-related facilities (e.g., pharmacy, diagnostic laboratory, etc.).

Participation as an Investigator in this study implies acceptance of potential inspection by government regulatory authorities and applicable University compliance and quality assurance offices.

## **11 Ethical Considerations**

This study is to be conducted according to US and international standards of GCP (Code of Federal Regulations [CFR] 21 CFR 312 and International Conference on Harmonization [ICH] guidelines), applicable government regulations and Institutional research policies and procedures.

This protocol and any amendments will be submitted to a properly constituted independent IRB, in agreement with local legal prescriptions, for formal approval of the study conduct. The decision of the IRB concerning the conduct of the study will be made in writing to the Investigator and a copy of this decision will be provided to the Sponsor before commencement of this study.

## **12 Study Finances**

### **12.1 Funding Source**

Research related costs will be paid for through an investigator initiated grant from Horizon Pharma. ACTIMMUNE will be provided by Horizon Pharma.

### **12.2 Conflicts of Interest**

Any Investigator who has a conflict of interest with this study (patent ownership, royalties, or financial gain greater than the minimum allowable by their institution, etc.) must refer to the Regents Policies on Individual Conflict of Interest Policy or Institutional Conflict of Interest Policy. These policies require University Faculty and staff to report external professional activities and business and significant financial interests related to his or her University activities by submitting a REPA (Report of External Professional Activities) at least once per year. Faculty and staff should also file a REPA when substantial changes in business or financial interests occur, when an activity that presents a potential conflict of interest is anticipated, or when submitting an application for research support or technology transfer, submitting research protocols to the IRB, or receiving financial contributions. All investigators will follow their University's conflict of interest policy.

## 13 Publications Plan

Neither the complete nor any part of the results of the study carried out under this protocol, nor any of the information provided by the Sponsor for the purposes of performing the study, will be published or passed on to any third party without the consent of the study Sponsor. Any Investigator involved with this study is obligated to provide the Sponsor with complete test results and all data derived from the study.

**1. Categorization of risk level (low, medium, or high) and a discussion of the relevant specific considerations.**

Risk Level:  Low

Moderate

High

Justification of Risk Level:

Potential for direct subject benefit.

**2. Specific information to be provided at the time of each periodic review and the bases for selecting this data set.**

**Enrollment Data:**

The investigator will prepare a periodic report to include **Local** target, interval and cumulative data in a tabular format as follows:

- Number of subjects screened
- Number of subjects enrolled
- Number of screen failures with reason for screen failure
- Dropout number with reason for dropout and stage of study at dropout
- Completion number
- Other study specific enrollment data such as subset enrolled in each group, site, etc. Specify below: enrollment at each site

**For Entire Study:**

- Number of subjects enrolled
- Completion number

**Local Adverse Event Reporting:**

- All study-related adverse events** (including loss of confidentiality and moderate-severe discomfort with study sample collection) with severity and attribution (possibly, probably or definitely related).
- The rates of routine illnesses (URI, headaches, muscle aches, etc.) and traumatic injuries are not expected to be different than usual and will not be reported or tracked as unexpected AEs but will be tracked and reported as AEs for the DSM Reports.

Serious Adverse Event and Unexpected Adverse Events:

- For all study-related serious adverse events (SAEs) and study-related unexpected adverse events (UAEs), the clinical summary will also be provided in a cumulative fashion.
- Due to the large number of disease-related SAEs such as  
fracture, bone pain, osteonecrosis, anemia, neutropenia, thrombocytopenia, cranial nerve impingement, and hypocalcemia,  
these serious adverse events will be tracked and evaluated by treatment group at each DSM periodic reporting but will not be reported by expedited reporting to the IRB.

**Entire Study Serious Adverse Event Reporting:**

- All **study-related** serious adverse events (SAEs) and **study-related** unexpected adverse events (UAEs)
- For all study-related serious adverse events (SAEs) and study-related unexpected adverse events (UAEs), the clinical summary will also be provided in a cumulative fashion.

The investigator will comply with the Policies for Reporting of Adverse Events to the local IRB that requires reporting of adverse events that in the opinion of the investigator may represent unanticipated problems involving risks to the other subjects in the research.

- The investigator will provide a tabulation of the unanticipated problems that meet the IRB reporting requirement with their evaluation of each events in the DSM Report

**Monitor's Review:**

- The investigator will provide the report to the Monitor at least 30 day before the CTRC due date for DSM Report submission.

- The Monitor will review the report and may request additional information from the investigator as needed to evaluate the safety and progress of the study. The monitor will submit the periodic report to the PI with the following by the due date.
  - Narrative summary of information presented.
  - Any concerns regarding adverse event rates, recruitment rates, drop-out rates, study integrity, etc
  - Any concerns regarding adverse event rates, recruitment rates, drop-out rates, study integrity, etc. with statement of how these concerns were resolved with the PI.
  - Recommendations for future study conduct (continuation, modification or termination).
- The PI will submit the DSM Report with the Monitor's review to the CTRC by the due date via iMedris.

### **3. Frequency of review, and rationale for recommended frequency.**

Frequency of Review: Every 6 months.

Rationale for Review Frequency: Limited number of subjects in the study (10 will be enrolled over 18 months) and the level of moderate risk.

### **4. Designation of individual(s) as independent monitor(s) reviewing the information. An explicit review of any conflict of interest issues should be presented.**

[name] will act as the Monitor for this clinical study. [name] is a faculty member at Harbor-UCLA with an appointment in the Department of Pediatrics, division of Endocrinology. She has expertise in the area of clinical trials and metabolic bone disease. She has no conflict of interest with the local PI or the study sponsor.

**APPENDIX B**

Schedule of Events (next page)

Schedule of Events										If ADA Positive	
	Screening a	Baseline	time from 1 st IFN- $\gamma$ 1b dose							time from last IFN- $\gamma$ 1b dose	
			3 weeks ( $\pm$ 2 days)	4 weeks ( $\pm$ 2 days)	6 weeks ( $\pm$ 2 days)	3 months ( $\pm$ 1 week)	6 months ( $\pm$ 1 week)	9 months ( $\pm$ 1 week)	12 months ( $\pm$ 1 week)	2-3 weeks	every 4-6 weeks
General											
Medical history	X	X				X	X		X		
Physical exam		X				X	X		X		
Genotype b		X									
RNA and DNA samples		X f				X	X		X		
Anthropometric measurements	X	X f				X	X		X		
Safety Measuresc											
Basic metabolic panel (BMP)	X	X		X	X	X	X	X	X		
Liver function tests (LFT)	X	X		X	X	X	X	X	X		
Urine pregnancy test (UPT) e	X	X				X	X	X	X		
Urinalysis (UA)	X	X		X	X	X	X	X	X		
ECHO with interpretation	X										
EKG with interpretation	X										
Anti-drug antibodies (ADA)			X	X	X	X	X		X	X	X
Bone Biomarker Testingd,g											
Formation Testing (bone specific alkaline phosphatase [BAP], type 1 procollagen [P1NP])	-	X				X	X		X		
Resorption testing (C-telopeptide [CTX], Tartrate resistant acid phosphatase type5b [TRAP5b])	-	X				X	X		X		
RANKL, OPG, CK-BB	-	X				X	X		X		
Endocrine Assessment											
Total 25-OH Vitamin D (25OHD)	-	X			X	X	X		X		
Serum ionized calcium	-	X				X	X		X		
Urine calcium: creatinine	-	X				X	X		X		
Intact parathyroid hormone (iPTH)	-	X				X	X		X		
Inflammatory/Immunology											
CBC with differential and platelets	-	X f				X	X		X		
Erythrocyte sedimentation rate (ESR)	-	X f				X	X		X		
Immunologic phenotyping (CD3, 4, 8, 14, 15, 16, 19, 34, 56) g	-	X				X	X		X		
Neuropsychological testing											
Pain assessment	-	X				X	X		X		
Quality of life survey	-	X				X	X		X		
Orthopedic assessment											
Dual energy X-ray absorptiometry (DXA) lumbar spine, total body, total hip and femoral neck (adults $\geq$ 18yrs only)	-	X				-	-		X		
Peripheral Quantitative CT (pQCT) left tibia	-	X				-	X		X		
In vitro osteoclast function assays – [name] Labh											
Gene expression – osteoclast marker genes	-	X				X	X		X		
Osteoclast activity – ability to release calcium phos from coated plate	-	X				X	X		X		
Infectious outcomes											
Number of hospitalizations in prior 3 months	-	X f				X	X		X		
Number of days treated with antibiotics in last 3 months	-	X f				X	X		X		
Type of infectious organism	-	X f				X	X		X		
Summary of samples collected per visit											
Serum (red top)	1	4	1		1	4	4		4	1	1
Plasma (purple top)	-	5	-		-	5	5		5	-	-
Urine (non-sterile)	1	1	-		-	1	1		1	-	-
Whole blood		1				1	1		1		

RANKL=Receptor activator of nuclear factor kappa-B ligand; OPG=osteoprotegerin; CK-BB=creatinine kinase isoenzyme BB.

a Screening visit evaluations will count for baseline evaluations where applicable.b Genetic testing for CLCN7, CAII, TCIRG1, OSTM1, and RANKL mutations will be done at the University of Minnesota if not already performed clinicallyc Subjects will be contacted on a weekly basis either by email or telephone to monitor safety during the initial 4 week dose escalation period.d Sample collection will be postponed if needed to ensure collection is more than 2 weeks since last fever ( $>100.4^{\circ}\text{F}$  [ $38^{\circ}\text{C}$ ] axillary) or fracture.e Post-menarchal females.f Height (for subjects  $<18$  years), CBC, and ESR will be obtain from the patient's medical record when available and number of hospitalizations and infectious data from the patient's medical record or if not available then the patient's recollection at the baseline visit.g Samples batch shipped every 3 months to [name]/[name] at UMNh Whole blood shipped overnight to [name] at UMN

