### 4.2 Secondary Hypotheses

The secondary hypotheses are:

1. Compared to baseline, treatment with IFN- $\gamma$ 1b will result in:
  - a. Decreased tibial volumetric bone mineral density (**vBMD**) and estimated bone strength measured by peripheral quantitative computed tomography (**pQCT**);
  - b. Decreased total body and lumbar spine areal BMD (**aBMD**) by dual-energy x-ray absorptiometry (**DXA**);
  - c. Increased levels of markers of bone remodeling (see Table 1);
  - d. Increased osteoclast activity by *in vitro* testing;
  - e. Increased white blood cell (**WBC**) and platelet counts in patients that have lower than expected blood counts at baseline.
  - f. Increased height standard deviation score (**SDS**) for participants <18 years with open growth plates;
  - g. Decreased inflammation measured by erythrocyte sedimentation rate (**ESR**);

[figure not shown]
- h. Decreased pain score (based on prior 4 weeks);
  - i. Increased physical function score (based on prior 4 weeks); and
2. Compared to the 12 months prior to study entry (based on medical record review or subject recollection), treatment with IFN- $\gamma$ 1b over 12 months will result in:
  - a. Decreased number of hospitalizations for infection;
  - b. Decreased number of days treated with antibiotics;
  - c. Beneficial change in WBC and platelet counts in patients who have lower than expected blood counts at baseline;
  - d. Beneficial change in ESR;
  - e. Increased height SDS for participants  $<18$  years with open growth plates; and
3. Patients will not develop neutralizing antibodies.

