## 5.3 Evaluations and study timeline

Table 1. Evaluations and study timeline

	Screening a	Baseline	# of months from 1 st IFN- $\gamma$ 1b treatment ( $\pm$ 1 week)		
			3	6	12
General					
• Medical history	X	X	X	X	X
• Physical exam		X	X	X	X
• Genotype b		X			
• Anthropometric measurements	X	X f	X	X	X
• RNA and DNA assays		X	X	X	X
Safety Measuresc					
• Basic metabolic panel (BMP)	X	X	X	X	X
• Liver function tests (LFT)	X	X	X	X	X
• Urine pregnancy test (UPT) e	X	X	X	X	X
• Urinalysis (UA)	X	X	X	X	X
• ECHO with interpretation	X				
• EKG with interpretation	X				

• Anti-drug antibodies (ADA) g		X	X	X	X
Bone Biomarker Testingd					
• Formation Testing (bone specific alkaline phosphatase [BAP], type 1 procollagen [P1NP])	-	X	X	X	X
• Resorption testing (C-telopeptide [CTX], Tartrate resistant acid phosphatase type5b [TRAP5b])	-	X	X	X	X
• RANKL, OPG, CK-BB	-	X	X	X	X
Endocrine Assessment					
• Total 25-OH Vitamin D (25OHD) h	-	X	X	X	X
• Serum ionized calcium	-	X	X	X	X
• Urine calcium: creatinine	-	X	X	X	X
• Intact parathyroid hormone (iPTH)	-	X	X	X	X
Inflammatory/Immunology					
• CBC with differential and platelets	-	X f	X	X	X
• Erythrocyte sedimentation rate (ESR)	-	X f	X	X	X
• Immunologic phenotyping (CD3, 4, 8, 14, 15, 16, 19, 34, 56)	-	X	X	X	X
Neuropsychological testing					
• Pain assessment	-	X	X	X	X
• Quality of life survey	-	X	X	X	X
Orthopedic assessment					
• Dual energy X-ray absorptiometry (DXA) lumbar spine, total body, total hip and femoral neck (adults $\geq 18$ yrs only)	-	X	-	-	X
• Peripheral Quantitative CT (pQCT) left tibia	-	X	-	X	X
In vitro osteoclast function assays – [name] Lab					
• Gene expression – osteoclast marker genes	-	X	X	X	X
• Osteoclast activity – ability to release calcium phos from coated plate	-	X	X	X	X
Infectious outcomes					
• Number of hospitalizations in prior 3 months	-	X f	X	X	X
• Number of days treated with antibiotics in last 3 months	-	X f	X	X	X
• Type of infectious organism	-	X f	X	X	X
RANKL=Receptor activator of nuclear factor kappa-B ligand; OPG=osteoprotegerin; CK-BB=creatinine kinase isoenzyme BB.					
a Screening visit evaluations will count for baseline evaluations where applicable. Screening visit will be within 3 months of baseline visit					

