b Genetic testing for CLCN7, CAII, TCIRG1, OSTM1, and RANKL mutations will be done at the University of Minnesota if not already performed clinically					
c Safety labs will also be obtained at weeks 4 and $6 \pm 2$ days, and month $9 \pm 1$ week; subjects will be contacted on a weekly basis either by email or telephone to monitor safety during the initial 4 week dose escalation period.					
d Sample collection will be postponed if needed to ensure collection is more than 2 weeks since last fever ( $>100.4^{\circ}\text{F}$ [ $38^{\circ}\text{C}$ ] axillary) or fracture.					
e Post-menarchal females.					
f Height (for subjects $<18$ years), CBC, and ESR will be obtain from the patient's medical record when available and number of hospitalizations and infectious data from the patient's medical record or if not available then the patient's recollection at the baseline visit.					
g ADA testing will also be performed at weeks 3 and $6 \pm 2$ days after the first dose, and 2-3 weeks after last dose, and then every 4-6 weeks until values return to baseline.					
h 25OHD level will be checked at 6 weeks as well.					

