#### **6.2.4 Serum Sample Procedure for Immunogenicity assays:**

Collect blood samples to analyze Anti-Drug Antibodies (ADA) to IFN- $\gamma$  and Neutralizing antibodies (Nab) to IFN- $\gamma$  levels using 4.0 mL blood collection tube tubes (BD Vacutainer® SST™ Serum Separation Tubes).

Collect a minimum of 2mL serum per time point described in Table 1.

After obtaining the blood sample, inverting the collection tube 5 times allow the blood to clot for 30 minutes at ambient temperature (19-24°C).

Centrifuge sample at approximately 1000-1300 RCF for 10 minutes at room temperature in a swinging bucket centrifuge.

Transfer duplicate serum aliquots of approximately equal volume (minimum of 2 x 100  $\mu$ L for ADA and 500  $\mu$ L for Nab with backup of 500  $\mu$ L per aliquot), using standard laboratory technique, into 2 polypropylene cryovials.

Secure a label to each storage tube. Labels should contain the following information:  
Sponsor: [name]

Sample Type: Human serum  
Sample date: DD-MMM-YYYY  
Sample time: XX:XX  
Protocol: 21549-01  
Subject Number: TBD  
Time point: TBD  
Serum Aliquot: TBD

Within 90 minutes of collection, store both aliquot samples upright at -20°C +/-5°C or -70°C ± 10°C.

Store at -70°C ± 10°C until collection of month 12 sample, then ship all study subject samples as follows. If samples are collected after month 12, then ship immediately to Intertek as follows.

Ship as separate shipments Serum Aliquot 1 and Serum Aliquot 2 samples for potential analysis of ADA and Nab with an adequate supply of dry ice via Fedex Monday through Wednesday to:

Attn: [name] (ADA samples) or [name] (Nab samples)  
Intertek Pharmaceutical Services  
[name]  
[name]

Provide an inventory log listing of all samples shipped with each shipment. Include a paper copy with the shipment and an electronic version via email to [name] ([[contact]](mailto:[contact])) and [name] ([[contact]](mailto:[contact])).

Send a shipment notification including a confirmation of the shipment date, courier name, and tracking information via email to [name] ([[contact]](mailto:[contact])) and [name] ([[contact]](mailto:[contact])).

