### 6.3.2 Laboratory Evaluations

Blood and urine will be collected at the time points described in Table 1.

CBCD, LFT, ESR, 25OHD, Calcium, iPTH, UA, urine ca:cr will be performed in real time by the Fairview Diagnostics Laboratory at UMN and at Quest for subjects seen at Harbor-UCLA at baseline, 3, 6, and 12 months. BMP, LFT, and UA will be performed at UMN, Quest, or the subject's local clinical lab at weeks 4 and 6, and month 9. Anti-drug antibody testing will be performed by Intertek Pharmaceutical Services at Baseline, at weeks 3 and 6, and months 3, 6 and 12, after the first dose, and 2-3 weeks after last dose, and then every 4-6 weeks until values return to baseline. Genetic testing for mutations in TCIRG1, CLCN7, CAII, OSTM1 and RANKL genes will be performed at the Baseline visit at the University of Minnesota for patients who have not had an osteopetrosis related mutation previously identified.

25OHD will be measured by liquid chromatography tandem mass spectrometry, and an attempt will be made to maintain levels between 30 ng/ml and 75 ng/ml. Treatment of vitamin D insufficiency/deficiency will be as follows:

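### Appendix B limits the 2-3-week post-dose antibody sample to ADA-positive subjects, while Table 1 and Section 6.3.2 take it from everyone; under month 12 batching, status cannot be known in time for early stoppers

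*Combined protocol and SAP*

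**What the plan says.** Secondary hypothesis 3 (Section 4.2) reads "Patients will not develop neutralizing antibodies". Three places set the sampling times that serve it.

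- **Section 6.3.2:** "Anti-drug antibody testing will be performed by Intertek Pharmaceutical Services at Baseline, at weeks 3 and 6, and months 3, 6 and 12", followed by samples "2-3 weeks after last dose, and then every 4-6 weeks until values return to baseline". No positivity condition is attached.
- **Table 1 (Section 5.3):** ADA is marked at Baseline and months 3, 6 and 12. Footnote g adds weeks 3 and 6 "and 2-3 weeks after last dose, and then every 4-6 weeks until values return to baseline". Again there is no condition.
- **Appendix B:** the two columns timed from the last dose stand under "If ADA Positive".

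On assay timing, Section 6.2.4 keeps the samples frozen "until collection of month 12 sample, then ship all study subject samples as follows", and Table 2 likewise batches ADA at the month 12 visit. Section 6.2.4 sends samples taken after month 12 to the laboratory at once. No section states an assay turnaround or how results get back to the sites.

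**The concern.** A subject who is ADA-negative, or whose samples have not been assayed, has a post-dose sample under Table 1 and Section 6.3.2 and none under Appendix B. A site working from the schedule of events would skip a sample that the body of the protocol requires, and a missed sample cannot be recovered.

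The condition also needs information that the batching rule may withhold. To apply it, the site must know the subject's ADA status 2-3 weeks after the last dose, yet nothing is shipped before month 12. What is at stake is detection of antibodies that first appear after dosing ends, in subjects not known to be positive. That is part of the evidence for hypothesis 3 in a study of 10.

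**Working it through.** The plan gives no computed figure for this hypothesis, and its sample size of 10 rests on feasibility (Section 7.2.1). The check is therefore a comparison of schedules and a timing calculation.

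**1. Schedules side by side (Appendix B as extracted)**

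| ADA time point | Table 1 with footnote g, and 6.3.2 | Appendix B |
|---|---|---|
| Baseline | yes | blank |
| Week 3 | yes | yes |
| Week 4 | no | yes |
| Week 6 | yes | yes |
| Months 3, 6, 12 | yes | yes |
| 2-3 weeks after last dose | all subjects | only if positive |
| Every 4-6 weeks after that | until return to baseline | only if positive |

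The condition on the last row is close to the body text in substance, since repeating until values return to baseline already implies that they are raised. The substantive conflict is the 2-3-week sample.

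**2. Subjects who stop drug early but stay in follow-up**

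Section 6.8 asks these subjects to remain in the study. Let L be the week of the last dose. The sample is due between weeks L + 2 and L + 3. Take the earliest shipment as week 52, which is the reading most favourable to the plan (each subject's samples go at that subject's own month 12 visit). The sample then precedes shipment by 52 - (L + 3) to 52 - (L + 2) weeks:

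- L = 10: 39 to 40 weeks
- L = 26: 23 to 24 weeks
- L = 40: 9 to 10 weeks

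For any last dose before week 49 (52 - 3), the whole sampling window closes before shipment, so status cannot be known.

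**3. Completers**

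Suppose the last dose falls on the day of the month 12 visit. The sample is due 14 to 21 days later. Shipping is Monday to Wednesday (Section 6.2.4), so the wait is 0 to 4 days. Transit is assumed to be 1 day. The laboratory then has between 14 - 4 - 1 = 9 and 21 - 0 - 1 = 20 days. Status is known in time only if the unstated turnaround is shorter than that.

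**4. Subjects who leave the study before month 12**

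Sections 5.4.8, 6.3.1 and 8.3.4 provide for withdrawal. These subjects have no month 12 sample, and Section 6.2.4 names no other event that releases their stored serum.

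**5. Baseline and week 4 cells**

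Both schedules carry eight ADA marks, so a single displaced mark would explain the blank Baseline and the extra week 4. Appendix B's serum tube row gives 4 tubes at Baseline, the same as at months 3, 6 and 12, where ADA is marked and the other serum tests are the same. That fits a planned Baseline draw. The tube row is blank at week 4, but it is also blank at month 9, where BMP and LFT are marked. It does not count every serum draw, so the week 4 blank is only suggestive.

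**6. What a lost sample costs**

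If n subjects have a post-dose sample and none is positive, the exact two-sided 95% upper limit for the positive rate is 1 - 0.025^(1/n). That is 30.8% for n = 10, 36.9% for n = 8 and 41.0% for n = 7. The smaller values of n are illustrations, not predictions.

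**The case against.** The best defence is that Appendix B does not govern. Section 6.2.4, the ADA procedure itself, refers to Table 1 for time points, as do Sections 6.2.1 and 6.3.2. A site that follows those sections will take the Baseline sample and the unconditional post-dose sample. This lowers the chance of harm but does not remove the conflict, because a schedule of events is a page that coordinators can be expected to use.

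A reader might infer that hypothesis 3 cannot be tested from Appendix B. The documents do not support that. Appendix B keeps six unconditional samples up to month 12, so antibodies arising on treatment would be seen, and uniformly negative results would support the hypothesis even without a baseline.

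A reader might also infer that all ten baseline references are missing. The tube row points the other way, and the blank cell may be a typing or extraction slip. If the page does show it blank, the loss would be real but limited: pre-existing antibodies could not be separated from new ones in a positive subject, and return to baseline would have no reference value.

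Finally, not everyone who stops drug early lacks a month 12 sample, because Section 6.8 asks such subjects to stay. Only those who leave altogether have no shipping trigger. For completers, the claim that status is unknown is not established; it depends on the turnaround.

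**Conclusion.** This is an internal inconsistency, wrong as written. For the 2-3-week post-dose ADA sample, Appendix B contradicts Table 1 footnote g and Section 6.3.2. The header is legible text, so this does not depend on how the table cells were extracted.

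The condition cannot be applied to subjects who stop drug before about week 49. For completers it works only if the assay is reported within roughly 9-20 days, given last dose on the day of the visit and 1 day in transit. Subjects who leave before month 12 have no stated route to assay.

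The number of subjects affected cannot be derived from the documents. Ten of ten is only a ceiling, reached if sites follow Appendix B and nobody is known to be positive when the sample falls due. The consequence is weaker evidence on antibodies first appearing after the last dose, not an untestable hypothesis. The Baseline and week 4 cells are a secondary point to verify.

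**What to change.** 1. In Appendix B, remove the positivity condition from the 2-3-week sample so that it matches Table 1 and Section 6.3.2. The 4-6-weekly samples can stay conditional on values not having returned to baseline.
2. In Section 6.2.4, add a shipping trigger at early withdrawal, so that stored serum from subjects without a month 12 sample is assayed. State there when results reach the sites. Extending the trigger to subjects who stop drug but stay in follow-up would also supply the results on which the 4-6-weekly samples depend.
3. Check the Appendix B ADA row on the printed page. If it shows a blank Baseline and a week 4 mark, correct the fixed time points to Baseline, weeks 3 and 6, and months 3, 6 and 12.

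The cost is a table correction and a sentence or two in Section 6.2.4. The sampling burden is at most one 4 mL draw per subject beyond Appendix B, which Table 1 and Section 6.3.2 already require. The sample size does not change.
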